28.2 Planned Interim Analysis

The interim assessment will be performed when the safety and immunogenicity data through Day 43 visit is available for 300 subjects in the Phase 2 component. The purpose of this interim assessment is determined a dose to be studied in the Phase 3 component.

The interim assessment will be performed by a third party who is not involved in the conduct of the study. The unblinded results summarized by treatment group and the final decision will be submitted to the Vietnamese MOH for their review prior to the resumption of the enrollment. No individual listing will be generated. This interim assessment will not otherwise alter the course of the trial and blinded status of the study.

Since the purpose of this interim assessment is to select the dose for the Phase 3 component and the final confirmatory analysis will be solely based on the data generated for the Phase 3 component only, there is no need to make an adjustment to the Type I error rate.

28.3 Final Analysis Plan

The Final Analysis Plan will be the responsibility of the CRO, and detailed in the Data Management Plan. The Plan will be developed by CRO and submitted to IVAC, PATH, and WHO for approval before implementation. The database will be locked and the analysis will be conducted only after all data has been entered and cleaned.

28.4 Timing/Reports

It is estimated that the database lock will occur about 8 weeks after the final visit of the last study participant and the clinical study report should be completed within 6 months from the final visit of the last study participant.

28.5 Study Record Retention

Study data will be kept for 15 years after completion of the study. No records will be destroyed without the written consent of IVAC. It is the responsibility of IVAC to inform the PI when these documents no longer need to be retained.

29 Protocol Deviations

A protocol deviation is any noncompliance with the clinical study protocol, GCP, or site procedures. The noncompliance may be either on the part of the subject, the investigator, or the study site staff. As a result of any deviations, corrective actions are to be developed by the site and implemented promptly. Trial procedures shall not be changed without the consent of IVAC. Insignificant violations of the protocol will be examined on an individual basis taking into account recorded information for the reason(s) that the deviation occurred.

It is the responsibility of the site to use continuous vigilance to identify and report deviations to IVAC in a timely manner after identification. If required, reports of protocol deviations must be sent to the research ethics committees overseeing the research. The PI and his/her staff are responsible for knowing and adhering to their research ethics committee's/IRB's requirements.

30 Human Resources

30.1 Human Resource for the Study

The study research team will be qualified by experience, education, and training to conduct their responsibilities on this study.

The study site will make arrangements with local health centers to adequately care for participants who experience side effects/illnesses that need care beyond what the study site can provide.

The research team may use commune health centers to prepare a list for potential subjects, keep contact with study subjects, conduct non-vaccination follow up visits, and conduct home visits (if needed).

30.2 Training Plan

All key personnel (those responsible for the design and conduct of this study) will have completed Human Subjects Protection and/or GCP Training, as appropriate to their role, prior to interaction with any

participants or to having access to their confidential study data. In addition, staff will be trained on any written procedures that pertain to their role in the study.

31 Clinical Study Report and Publication Policy

31.1 Clinical Study Report

A Clinical Study Report (CSR) comprised of text and results tables reflecting all safety and immunogenicity data will be generated by IVAC or its designates. The CSR will be compliant with ICH E: 3 guidelines.

All data, documents, recordings, and information transferred to any contractor or obtained or prepared by any contractor, his consultants or persons associated by contractual relationships with any contractor during the trials, belong to IVAC.

All confidential information communicated to the Principal Investigator by IVAC shall be kept strictly confidential by him/her or any other person connected with the study and shall not be disclosed, either orally or in written form, by him/her or such person to any third party without prior written consent of the organization of which the information is the exclusive property.

Following completion of the clinical study report, the investigators, working with IVAC and representatives, are expected to publish the results, negative or positive, of this research in peer-reviewed scientific journal(s). IVAC may not prohibit the public dissemination of the results of this trial; details of the publication plan are specified in the Agreement between IVAC and NIHE.

APPENDIX A

WHO Summary Table of Whole Virion A/H5N1 Influenza Vaccination Schedule by Manufacturer

(Source: www.who.int/entity/immunization/research/development/flu_trials_tables/en/)

Producer	Adjuvant	Dose	Schedule	% Responders at a Specified Titer	Seroconversion Rate	GMT Increase
Baxter (Czech Republic/Austria)	Al(OH)3	3.75, 7.5, 15, 30, 45	Two doses at day 0, 21	NT \geq 20 after two doses: 66% (30 μ g+Alum) 61% (15 μ g+Alum) 64% (7.5 μ g+Alum) 69% (3.75 μ g+Alum) 71% (15 μ g no Alum) 76% (7.5 μ g no Alum)	NT \geq 4 fold increase after 2 doses: 51% (7.5 μ g+Alum) 55% (3.75 μ g+Alum) 69% (7.5 μ g no Alum)	Fold increase in NT after 2 doses: 4.6 (30 μ g+Alum) 3.9 (15 μ g+Alum) 4.0 (7.5 μ g+Alum) 4.4 (3.75 μ g+Alum) 5.7 (15 μ g no Alum) 5.3 (7.5 μ g no Alum)
Baxter (Czech Republic/Austria)	Al(OH)3; None	7.5, 15, 45	Two doses	NI \geq 40 after 2 doses: 40% (45 μ g no Alum) 12% (15 μ g+Alum) 20% (15 μ g no Alum) 8% (7.5 μ g+Alum) 19% (7.5 μ g no Alum)	NI \geq 4 fold increase after 2 doses: 40% (45 μ g no Alum) 12% (15 μ g+Alum) 18% (15 μ g no Alum) 8% (7.5 μ g+Alum) 19% (7.5 μ g no Alum)	No data
Baxter (Czech Republic/Austria)	Al(OH)3	3.75, 7.5, 15, 30 - priming; 7.5 - booster	Priming: two doses; Booster: one dose 12-17 months after priming	NT \geq 20 after boost against strains: 97% A/Indonesia 96% A/vietnam 96% A/turkey/Turkey 83% A/Anhui	No data	No data
Biken, Japan	Al(OH)3	1.7, 5, 15	Two doses at day 0, 21	NT \geq 40 after 2 doses: IM SC 95% 84% (15 μ g+Alum) 70% 80% (5 μ g+Alum) 60% 53% (1.7 μ g+Alum)	NT \geq 4 fold increase after 2 doses: IM SC 95% 79% (15 μ g+Alum) 65% 75% (5 μ g+Alum) 40% 47% (1.7 μ g+Alum)	Fold Increase in NT after 2 doses: IM SC 14.0 13.3 (15 μ g+Alum) 7.0 5.7 (5 μ g+Alum) 2.9 3.4 (1.7 μ g+Alum)
Biken, Japan	Al(OH)3	5, 15	Two doses at day 0, 21	NT \geq 40 after 2 doses = 85% (15 μ g+Alum) 57% (5 μ g+Alum)	NT \geq 4 fold increase in NT after 2 doses: 71% (15 μ g+Alum) 45% (5 μ g+Alum)	Fold increase in NT after 2 doses: 4.7 (15 μ g+Alum) 2.6 (5 μ g+Alum)
Denka Seiken, Japan	Al(OH)3	1.7, 5, 15	Two doses at day 0, 21	No data	No data	No data
Denka Seiken, Japan	Al(OH)3	5, 15	Two doses at day 0, 21	No data	No data	No data

Producer	Adjuvant	Dose	Schedule	% Responders at a Specified Titer	Seroconversion Rate	GMT Increase
Kitasato Institute, Japan	Al(OH)3	1.7, 5, 15	Two doses at day 0, 21	No data	NT \geq 4 fold increase after 2 doses: IM SC 100% 74% (15 μ g+Alum) 75% 58% (5 μ g+Alum) 50% 25% (1.7 μ g+Alum)	Fold Increase in NT after 2 doses: SC 41.5 (15 μ g+Alum) 29.9 (5 μ g+Alum) 12.7 (5 μ g+Alum)
Kitasato Institute, Japan	Al(OH)3	5, 15	Two doses at day 0, 21	No data	NT \geq 4 fold increase after 2 doses: 81% (15 μ g+Alum) 65% (5 μ g+Alum)	Fold increase in NT after 2 doses: 5.1 (15 μ g+Alum) 3.7 (5 μ g+Alum)
Kaketsuken, Japan	Al(OH)3	1.7, 5, 15	Two doses at day 0, 21	NT \geq 40 after 2 doses: IM SC 45% 37% (15 μ g+Alum) 20% 5% (5 μ g+Alum)	NT \geq 4 fold increase after 2 doses: IM SC 75% 68% (15 μ g+Alum) 50% 20% (5 μ g+Alum)	Fold increase in NT after 2 doses: IM SC 6.3 4.8 (15 μ g+Alum) 2.9 1.6 (5 μ g+Alum)
Kaketsuken, Japan	Al(OH)3	5, 15	Two doses at day 0, 21	NT \geq 40 after 2 doses: 77% (15 μ g+Alum) 53% (5 μ g+Alum)	NT \geq 4 fold increase after 2 doses: 86% (15 μ g+Alum) 56% (5 μ g+Alum)	Fold increase in NT after 2 doses: 8.9 (15 μ g+Alum) 4.3 (5 μ g+Alum)
Biken and Kitazato Institute, Japan	Al(OH)3	15	Two doses at day 0, 21	NT \geq 40 after 2 doses with Indonesia against: Indonesia Vietnam 74% 15%	NT \geq 4 fold increase after 2 doses with Anhui Ag against: Anhui Vietnam 82% 74%	Fold increase in NT after 2 doses with Indonesia against: Indonesia Vietnam 9.4 2.0
Biken and Kitazato Institute, Japan	Al(OH)3	15	Priming: two doses with Vietnam strain; Booster: single dose two years after priming	NT \geq 40 after boosting with Indonesia against: Indonesia Vietnam 92% 97%	NT \geq 4 fold increase after boosting with Anhui Ag: against: Anhui Vietnam 94% 1%	Fold increase in NT after boosting with Indonesia: against: Indonesia Vietnam 36.7 23.1
Biken and Kitazato Institute, Japan	Al(OH)3	15	Two doses at day 0, 21	No data	No data	No data

Producer	Adjuvant	Dose	Schedule	% Responders at a Specified Titer	Seroconversion Rate	GMT Increase
GSK Biologicals, Belgium	AlPO4; Al(OH)3	3.8, 7.5, 15, 27	Two doses at day 0, 21	HI≥40 after 2 doses: 90% (27mg+Alum) 71% (15mg+Alum) 63% (7.5mg+Alum) 69% (3.8mg+Alum) 71% (27mg non Alum) 70% (15mg non Alum) 58% (7.5mg non Alum) 51% (3.8mg non Alum)	HI≥4 fold increase after 2 doses: 90% (27mg+Alum) 71% (15mg+Alum) 63% (7.5mg+Alum) 67% (3.8mg+Alum) 71% (27mg no Alum) 0% (15mg no Alum) 58% (7.5mg no Alum) 51% (3.8mg+ no Alum)	Fold increase in HI after 2 doses: 32.4 (27mg+Alum) 12.4 (15mg+Alum) 9.1 (7.5mg+Alum) 10.5 (3.8mg+Alum) 13.0 (27mg non Alum) 10.9 (15mg non Alum) 7.9 (7.5mg non Alum) 5.7 (3.8mg non Alum)
Omninvest, Hungary	AlPO4	6	Single dose	HI≥40 = 63.7%	HI≥4 fold increase = 63.7%	HI fold increase in HI = 5.6
Omninvest, Hungary	AlPO4	6	Single dose	HI≥40: Adults Elderly 79% 61%	HI≥4 fold increase: Adults Elderly 91% 68%	HI fold increase: Adults Elderly 18.7 10.9
Omninvest, Hungary	AlPO4	6	Single dose	HI≥40: 75%	HI≥40: 75%	Fold increase in HI: 16.9
Omninvest, Hungary	AlPO4	3.5, 6, 12	Single or two doses	HI≥64 (adults) = 71% (12µg+Alum, 1 dose) 72% (6µg+Alum, 1 dose) 38% (3.5µg+Alum, 1 dose) 72% (3.5µg+Alum, 2 doses) HI≥64 (elderly) = 67% (12µg+Alum, 1 dose) 65% (6µg+Alum, 1 dose) 35% (3.5µg+Alum, 1 dose) 61% (3.5µg+Alum, 2 doses)	HI≥4 fold increase (adults) = 71% (12µg+Alum, 1 dose) 72% (6µg+Alum, 1 dose) 38% (3.5µg+Alum, 1 dose) 72% (3.5µg+Alum, 2 doses) HT≥4 fold increase (elderly) = 67% (12µg+Alum, 1 dose) 65% (6µg+Alum, 1 dose) 35% (3.5µg+Alum, 1 dose) 61% (3.5µg+Alum, 2 doses)	Fold increase in HI (adults) = 22.8 (12µg+Alum, 1 dose) 21.1 (6µg+Alum, 1 dose) 11.1 (3.5µg+Alum, 1 dose) 19.9 (3.5µg+Alum, 2 doses) Fold increase in HI (elderly) = 15.2 (12µg+Alum, 1 dose) 14.8 (6µg+Alum, 1 dose) 10.1 (3.5µg+Alum, 1 dose) 14.5 (3.5µg+Alum, 2 doses)

Producer	Adjuvant	Dose	Schedule	% Responders at a Specified Titer	Seroconversion Rate	GMT Increase
Sinovac Biotech, China	Al(OH)3	1.25, 2.5, 5, 10	Priming: two doses at day 0, 28; Booster: one dose	HI \geq 40 after: priming 78% (10 μ g+Alum) 33% (5 μ g+Alum) 29% (2.5 μ g+Alum) 13% (1.25 μ g+Alum) boosting 90% 79% 31% 29%	HI \geq 4 fold increase after: priming 78% (10 μ g+Alum) 33% (5 μ g+Alum) 24% (2.5 μ g+Alum) 13% 79% (5 μ g+Alum) 19% (2.5 μ g+Alum) 24% (1.25 μ g+Alum)	Fold increase in HI after priming: 11.5 (10 μ g+Alum) 4.9 (5 μ g+Alum) 2.7 (2.5 μ g+Alum) 2.7 (1.25 μ g+alum)
Sinovac Biotech, China	Al(OH)3	5, 10, 15	Two doses at day 0, 14 or 0, 28	HI \geq 40 after 2 doses: 90% (15 μ g+Alum) 78% (10 μ g+Alum) 54% (5 μ g+Alum) NT \geq 40 after 2 doses: 100% (15 μ g+Alum) 96% (10 μ g+Alum) 94% (5 μ g+Alum)	HI \geq 4 fold increase after 2 doses: 90% (15 μ g+Alum) 78% (10 μ g+Alum) 53% (5 μ g+Alum) HT \geq 4 fold increase after 2 doses: 100% (15 μ g+Alum) 92% (10 μ g+Alum) 91% (5 μ g+Alum)	Fold increase in HI after 2 doses: 18.2 (15 μ g+Alum) 12.4 (10 μ g+Alum) 6.3 (5 μ g+Alum) Fold increase in NT after 2 doses: 30.4 (15 μ g+Alum) 21.9 (10 μ g+Alum) 13.5 (5 μ g+Alum)
Sinovac Biotech, China	Al(OH)3	5	Two doses at day 0, 28	HI \geq 40 after two doses: 45%	HI \geq 4 fold increase after 2 doses: 45%	Fold increase in HI after two doses: 6.0
Sinovac Biotech, China	Al(OH)3	10	Two doses at day 0, 28	HI \geq 40 49% : NT	HI \geq 4 fold increase after 2 doses: 48%	Fold increase in HI: 5.5
Sinovac Biotech, China	Al(OH)3	1.25, 2.5, 5, 10	Priming: two doses; Booster: one dose 12 months after priming	\geq 40 after 3 doses: HI 90% (10 μ g+Alum) 79% (5 μ g+Alum) 31% (2.5 μ g+Alum) 29% (1.25 μ g+Alum) NT 100% 93% 81% 53%	\geq 4 fold increase after 3 doses: HI 80% (10 μ g+Alum) 79% 79% (5 μ g+Alum) 12% 62% (2.5 μ g+Alum) 24% 47% (1.25 μ g+Alum)	No data
Vabiotech, Vietnam	Al(OH)3	30	Two doses at day 0, 28	HI \geq 40 after 2 doses: 95.8% (30 μ g+Alum)	HI \geq 4 fold increase after 2 doses: 95.8% (15 μ g+Alum)	Fold increase in HI after 2 doses: 9.1 (30 μ g+Alum)

Producer	Adjuvant	Dose	Schedule	% Responders at a Specified Titer	Seroconversion Rate	GMT Increase
Vabiotech, Vietnam	Al(OH)3	3.75, 7.5, 15, 30, 45	Two doses at day 0, 28	HI \geq 40 after doses: 1 2 46% 97% (45 μ g) 42% 94% (30 μ g) 29% 83% (15 μ g) 26% 76% (7.5 μ g) 21% 61% (3.75 μ g)	HI \geq 4 fold increase after doses: 1 2 46% 97% (45 μ g) 42% 94% (30 μ g) 29% 83% (15 μ g) 26% 76% (7.5 μ g) 21% 61% (3.75 μ g)	Fold increase in HI after doses: 1 2 2.9 14.2 (45 μ g) 2.7 10.1 (30 μ g) 1.6 6.1 (15 μ g) 1.8 3.9 (7.5 μ g) 1.6 3.1 (3.75%)
Vabiotech, Vietnam	Al(OH)3	30	Two doses at day 0, 28	HI \geq 40 after 2 doses: 92% with strain 30408, Clade 1 79% with strain 31244, Clade 2	HI \geq 4 fold increase after 2 doses: 93% with strain 30408, Clade 1 81% with strain 31244, Clade 2	Fold increase after 2 doses: 8.1 with strain 30408, Clade 1 5.3 with strain 31244, Clade 2
RIBSP, Kazakhstan	AL(OH)3	7.5, 15	Two doses at day 0, 21	HI \geq 40 after 1 and 2 doses: 1 2 67% 89% (15 μ g+ Alum) 17% 67% (7.5 μ g+Alum)	HI \geq 4 fold increase after 1 and 2 doses: 1 2 91% 89% (15 μ g+ Alum) 67% 75% (7.5 μ g+Alum)	Fold increase in HI after 1 and 2 doses: 1 2 8.0 10.6 (15 μ g+ Alum) 3.3 5.7 (7.5 μ g+Alum)
RIBSP, Kazakhstan	AL(OH)3	7.5, 15	Single dose	HI \geq 40 after 1 dose: 58% (15 μ g+ Alum) 53% (7.5 μ g+Alum)	HI \geq 4 fold increase after 1 dose: 70% (15 μ g+ Alum) 55% (7.5 μ g+Alum)	Fold increase in HI after 1 dose: 4.7 (15 μ g+ Alum) 3.5 (7.5 μ g+Alum)
Netherlands Vaccine Institute	None	15	Two doses at day 0, 21	HI \geq 40 after 2 doses: 69%	HI \geq 4 fold increase after 2 doses: 69%	Fold increase in HI after 2 doses: 8.9

APPENDIX B**IVACFLU-A/H5N1**
TABLE OF GRADING SEVERITY FOR CERTAIN EVENTS¹**I. Instructions and Clarifications****Estimating Severity Grade for Parameters Not Identified in the Table**

In order to grade a clinical AE that is not identified in the DAIDS AE grading table, refer to the protocol.

Determining Severity Grade for Parameters “Between Grades”

If the severity of a clinical AE could fall under either one of two grades (e.g., the severity of an AE could be either Grade 2 or Grade 3), select the higher of the two grades for the AE. If a laboratory value that is graded as a multiple of the ULN or LLN falls between two grades, select the higher of the two grades for the AE. For example, Grade 1 is $2.5 \times$ ULN and Grade 2 is $2.6 \times$ ULN for a parameter. If the lab value is $2.53 \times$ ULN (which is between the two grades), the severity of this AE would be Grade 2, the higher of the two grades.

Values Below Grade 1

Any laboratory value that is between either the LLN or ULN and Grade 1 should not be graded.

Determining Severity Grade when Local Laboratory Normal Values Overlap with Grade 1 Ranges

In these situations, the severity grading is based on the ranges in the DAIDS AE Grading Table, even when there is a reference to the local lab LLN.

For example: Phosphate, Serum, Low, Adult and Pediatric > 14 years Grade 1 range is $2.50 \text{ mg/dL} - < \text{LLN}$. A particular laboratory’s normal range for Phosphate is $2.1 - 3.8 \text{ mg/dL}$. A participant’s actual lab value is 2.5. In this case, the value of 2.5 exceeds the LLN for the local lab, but will be graded as Grade 1 per DAIDS AE Grading Table.

¹ Based On The DAIDS Table For Grading the Severity of Adult And Pediatric Adverse Events, Version 2.0, November 2014; and Guidance For Industry: Toxicity Grading Scale for Healthy Adult and Adolescent Volunteers Enrolled in Preventive Vaccine Clinical Trials; FDA, 2007.

II. Definitions of Terms Used in the Table:

Basic Self-care	Functions Adult
	Activities such as bathing, dressing, toileting, transfer/movement, continence, and feeding.
LLN	Lower limit of normal
Medical Intervention	Use of pharmacologic or biologic agent(s) for treatment of an AE
NA	Not Applicable
Operative Intervention	Surgical OR other invasive mechanical procedures.
ULN	Upper limit of normal
Usual Social & Functional Activities	Adult Adaptive tasks and desirable activities, such as going to work, shopping, cooking, use of transportation, pursuing a hobby, etc.

PARAMETER	GRADE 1 MILD	GRADE 2 MODERATE	GRADE 3 SEVERE	GRADE 4 POTENTIALLY LIFE-THREATENING
ESTIMATING SEVERITY GRADE				
SYSTEMIC				
Acute Allergic Reaction	Localized urticaria (wheals) with no medical intervention indicated	Localized urticaria with intervention indicated OR Mild angioedema with no intervention indicated	Generalized urticaria OR Angioedema with intervention indicated OR Symptoms of mild bronchospasm	Acute anaphylaxis OR Life-threatening bronchospasm OR Laryngeal edema
Chills	Symptoms causing no or minimal interference with usual social & functional activities	Symptoms causing greater than minimal interference with usual social & functional activities	Symptoms causing inability to perform usual social & functional activities	NA
Fatigue or Malaise Report only one	Symptoms causing no or minimal interference with usual social & functional activities	Symptoms causing greater than minimal interference with usual social & functional activities	Symptoms causing inability to perform usual social & functional activities	Incapacitating symptoms of fatigue or malaise causing inability to perform basic self-care functions
Arthralgia (Joint Pain)	Joint pain causing no or minimal interference with usual social & functional activities	Joint pain causing greater than minimal interference with usual social & functional activities	Joint pain causing inability to perform usual social & functional activities	Incapacitating joint pain causing inability to perform basic self-care functions
Fever (non-axillary temperatures only)	38.0 to < 38.6°C	≥ 38.6 to < 39.3°C	≥ 39.3 to < 40.0°C	≥ 40.0°C
Fever (axillary)	37.7 – 38.1°C	38.2 – 38.8°C	38.9 – 40.0°C	> 40.0°C
Nausea	Transient (< 24 hours) or intermittent AND No or minimal interference with oral intake	Persistent nausea resulting in decreased oral intake for 24 to 48 hours	Persistent nausea resulting in minimal oral intake for > 48 hours OR Rehydration indicated (e.g., IV fluids)	Life-threatening consequences (e.g., hypotensive shock)
Vomiting	Transient or intermittent AND No or minimal interference with oral intake	Frequent episodes with no or mild dehydration	Persistent vomiting resulting in orthostatic hypotension OR Aggressive rehydration indicated (e.g., IV fluids)	Life-threatening consequences (e.g., hypotensive shock)
Headache	Symptoms causing no or minimal interference with usual social & functional activities	Symptoms causing greater than minimal interference with usual social & functional activities	Symptoms causing inability to perform usual social & functional activities	Symptoms causing inability to perform basic self-care functions OR Hospitalization indicated OR Headache with significant impairment of alertness or other neurologic function

PARAMETER	GRADE 1 MILD	GRADE 2 MODERATE	GRADE 3 SEVERE	GRADE 4 POTENTIALLY LIFE-THREATENING
INJECTION SITE REACTIONS				
Injection Site Pain or Tenderness Report only one	Pain or tenderness causing no or minimal limitation of use of limb	Pain or tenderness causing greater than minimal limitation of use of limb	Pain or tenderness causing inability to perform usual social & functional activities	Pain or tenderness causing inability to perform basic self-care function OR Hospitalization indicated
Injection Site Erythema or Redness Report only one > 15 years of age	2.5 to < 5 cm in diameter OR 6.25 to < 25 cm ² surface area AND Symptoms causing no or minimal interference with usual social & functional activities	≥ 5 to < 10 cm in diameter OR ≥ 25 to < 100 cm ² surface area OR Symptoms causing greater than minimal interference with usual social & functional activities	≥ 10 cm in diameter OR ≥ 100 cm ² surface area OR Ulceration OR Secondary infection OR Phlebitis OR Sterile abscess OR Drainage OR Symptoms causing inability to perform usual social & functional activities	Potentially life-threatening consequences (e.g., abscess, exfoliative dermatitis, necrosis involving dermis or deeper tissue)
Injection Site Induration or Swelling Report only one > 15 years of age	Same as for Injection Site Erythema or Redness, > 15 years of age	Same as for Injection Site Erythema or Redness, > 15 years of age	Same as for Injection Site Erythema or Redness, > 15 years of age	Same as for Injection Site Erythema or Redness, > 15 years of age

LABORATORY							
PARAMETER	GRADE 1 MILD	GRADE 2 MODERATE	GRADE 3 SEVERE	GRADE 4 POTENTIALLY LIFE-THREATENING			
HEMATOLOGY		Standard International Units are listed in italics					
Hemoglobin (Hgb)							
Comment: The conversion factor used to convert g/dL to mmol/L is 0.6206 and is the most commonly used conversion factor. For grading hemoglobin results obtained by an analytic method with a conversion factor other than 0.6206, the result must be converted to g/dL using the appropriate conversion factor for the particular laboratory.							
Hemoglobin, Low (g/dL; mmol/L) ≥ 13 years of age (male only)	10.0 to 10.9 6.19 to 6.76	9.0 to < 10.0 5.57 to < 6.19	7.0 to < 9.0 4.34 to < 5.57	< 7.0 < 4.34			
≥ 13 years of age (female only)	9.5 to 10.4 5.88 to 6.48	8.5 to < 9.5 5.25 to < 5.88	6.5 to < 8.5 4.03 to < 5.25	< 6.5 < 4.03			
Platelets, Decreased (cells/mm ³ ; cells/L)	100,000 to < 124,999 100,000 x 10⁹ to < 124,999 x 10⁹	50,000 to < 100,000 50,000 x 10⁹ to < 100,000 x 10⁹	25,000 to < 50,000 25,000 x 10⁹ to < 50,000 x 10⁹	< 25,000 < 25,000 x 10⁹			
WBC, Decreased (cells/mm ³ ; cells/L) > 7 days of age	2,000 to 2,499 2,000 x 10⁹ to 2,499 x 10⁹	1,500 to 1,999 1,500 x 10⁹ to 1,999 x 10⁹	1,000 to 1,499 1,000 x 10⁹ to 1,499 x 10⁹	< 1,000 < 1,000 x 10⁹			

LABORATORY				
PARAMETER	GRADE 1 MILD	GRADE 2 MODERATE	GRADE 3 SEVERE	GRADE 4 POTENTIALLY LIFE-THREATENING
CHEMISTRIES		Standard International Units are listed in italics		
ALT or SGPT, High Report only one	1.25 to < 2.5 x ULN	2.5 to < 5.0 x ULN	5.0 to < 10.0 x ULN	≥ 10.0 x ULN
Total Bilirubin, High > 28 days of age	1.1 to < 1.6 x ULN	1.6 to < 2.6 x ULN	2.6 to < 5.0 x ULN	≥ 5.0 x ULN
Creatinine, High	1.1 to 1.3 x ULN	> 1.3 to 1.8 x ULN OR Increase of > 0.3 mg/dL above baseline	> 1.8 to < 3.5 x ULN OR Increase of 1.5 to < 2.0 x above baseline	≥ 3.5 x ULN OR Increase of ≥ 2.0 x above baseline
Total Protein (FDA Table)	5.5 – 6.0	5.0 – 5.4	< 5.0	--

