- Any condition in the opinion of the investigator that would increase the health risk of the subject if he/she participates in the study or interfere with the evaluation of the study objectives.

Note: Minor out-of-range laboratory values no greater than Grade 1 (see toxicity table in Appendix) will not be considered to be exclusionary at screening.

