9.2 Methods and Timing for Assessing and Recording Safety Parameters

9.2.1 Adverse Events

An AE is defined as any untoward medical occurrence in a patient or clinical investigation participant administered a pharmaceutical product, which does not necessarily have a causal relationship with this treatment. An AE can therefore be any unfavorable and unintended sign (including an abnormal laboratory finding), symptom, or disease temporally associated with the use of a medicinal product,

whether or not considered related to the medicinal product. Information to be collected on AEs includes event description, time of onset, clinician's assessment of severity, relationship to study product, and time of resolution/stabilization of the event. AE assessment should be made only by those with the training and authority to make a diagnosis.

In this protocol, laboratory results are considered AEs when the result is Grade 2 or above.

Any medical condition that was present at the time that the subject was enrolled should not be reported as an AE, but should be reported as a pre-existing condition on the Medical History Form. However, if this condition occurs with greater frequency or severity during the study, it should be recorded as an AE.

AEs, including laboratory abnormalities that are Grade 2 and above, should always be assessed for severity and relationship to study products.

This study will collect and record solicited local and systemic reactogenicity and unsolicited AEs. For clarity, solicited reactogenicity refers to AEs specifically asked about during the 7-day post-vaccination period. Unsolicited events are those not specifically solicited, but may be reported by the subject at any time or observed by study staff while the subject is at a clinic for a study visit. If a new solicited event is reported by the subject outside of the 7-day post-vaccination window, this event will be recorded as an "unsolicited AE" because it will be outside of the 7-day window for collection of solicited reactogenicity.

SAEs are defined in Section 9.2.8.

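### In Appendix B the per-litre limits for low platelets and white cells are 1,000 times the per-mm³ limits in the same cells, so the two unit lines contradict each other

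*Protocol*

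**What the plan says.** The hematology part of Appendix B states that "Standard International Units are listed in italics". The platelet row is headed "Platelets, Decreased (cells/mm ³ ; cells/L", and the white-cell row carries the same pair of units. Each grade cell therefore has a mm³ line followed by a per-litre line. For Grade 2 platelets these are "50,000 to < 100,000" and "50,000 x 10⁹ to < 100,000 x 10⁹". For white cells the per-litre line is "2,000 x 10⁹ to 2,499 x 10⁹" at Grade 1 and "1,500 x 10⁹ to 1,999 x 10⁹" at Grade 2.

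Two rules in the body of the protocol depend on these grades. The note at the end of Section 5.3 reads "Minor out-of-range laboratory values no greater than Grade 1 (see toxicity table in Appendix) will not be considered to be exclusionary at screening". Section 9.2.1 reads "In this protocol, laboratory results are considered AEs when the result is Grade 2 or above". Sections 9.2.4 and 9.2.9 apply the same Grade 2 threshold but word it for out-of-range results. Section 8.2.1 says that reference ranges are fixed before enrollment and that the table serves to grade results falling outside them. Under that section platelets and white cells are measured in Phase 2 subjects only, at S1 and on Days 8, 22 and 29.

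**The concern.** The per-litre line repeats the mm³ number and adds a factor of 10⁹, although the conversion factor is 10⁶. One count can then get two different grades from a single cell, depending on the unit in which it is reported.

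The table is in active use. A Grade 2 result has to be recorded as an adverse event and assessed for relatedness and clinical significance, and the Phase 2 safety data go to the DSMB and are one of the factors in dose selection. If results came per litre and the printed line were followed, mildly low counts would enter those summaries as Grade 4. If staff saw the problem and corrected it informally, the thresholds applied would not be the ones in the approved protocol, and nothing in the documents would show which had been used.

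**Working it through.** **Inputs.** All limits come from the platelet and white-cell rows of Appendix B. The conversion is 1 L = 10⁶ mm³, so cells/L = cells/mm³ x 10⁶.

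**Step 1: try to reproduce the printed per-litre figures.** For the lower Grade 2 platelet limit, 50,000/mm³ x 10⁶ = 5 x 10¹⁰/L = 50 x 10⁹/L. The table prints 50,000 x 10⁹/L. The ratio is 50,000 / 50 = 1,000, so the printed figure is not reproduced.

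**Step 2: repeat for all ten distinct limits.**

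| Row | Limit per mm³ | Converted, x 10⁹/L | Printed, x 10⁹/L | Ratio |
|---|---|---|---|---|
| Platelets | 124,999 | 124.999 | 124,999 | 1,000 |
| Platelets | 100,000 | 100 | 100,000 | 1,000 |
| Platelets | 50,000 | 50 | 50,000 | 1,000 |
| Platelets | 25,000 | 25 | 25,000 | 1,000 |
| WBC | 2,499 | 2.499 | 2,499 | 1,000 |
| WBC | 2,000 | 2.000 | 2,000 | 1,000 |
| WBC | 1,999 | 1.999 | 1,999 | 1,000 |
| WBC | 1,500 | 1.500 | 1,500 | 1,000 |
| WBC | 1,499 | 1.499 | 1,499 | 1,000 |
| WBC | 1,000 | 1.000 | 1,000 | 1,000 |

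**Step 3: is a decimal comma intended?** If the comma in the per-litre line is read as a decimal mark, every ratio becomes exactly 1.0, which probably explains how the figures arose. The table as printed does not allow that reading: the mm³ line of the same cell uses the comma for thousands, and the hemoglobin rows just above use a decimal point.

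**Step 4: is the fault confined to these rows?** The hemoglobin rows convert g/dL to mmol/L by 0.6206. Two examples: 10.9 x 0.6206 = 6.765 against a printed 6.76, and 10.4 x 0.6206 = 6.454 against a printed 6.48. All eight hemoglobin limits agree to within about 0.03 mmol/L. There is no 1,000-fold error there.

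**Step 5: what happens to a low count.** Take an assumed platelet count of 110 x 10⁹/L.
- Per mm³ this is 110 x 10⁹ / 10⁶ = 110,000. It lies between 100,000 and 124,999, so it is Grade 1 and not an adverse event.
- Per litre, 110 x 10⁹ is below the printed Grade 4 limit of 25,000 x 10⁹, so it is Grade 4 and an adverse event.

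**Step 6: how far the printed line is from any plausible count.** To escape Grade 4 on the per-litre line, platelets would have to reach 25,000 x 10⁹ / 10⁶ = 25,000,000/mm³. That is 200 times the point, about 125,000/mm³, above which the mm³ line assigns no grade. White cells would have to reach 1,000 x 10⁹ / 10⁶ = 1,000,000/mm³, which is 400 times the corresponding point of about 2,500/mm³. So the result in Step 5 does not depend on the count chosen: every low count grades as 4.

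**The case against.** The arithmetic is not in dispute. The case on the other side is about how much follows from it, and most of that case stands.

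- **Grading of normal counts.** A reader might infer that every healthy subject's count becomes a Grade 4 adverse event, in all 300 Phase 2 subjects at every blood draw. The documents do not support this. Section 8.2.1 sends out-of-range results to the table, and Sections 9.2.4 and 9.2.9 define laboratory adverse events among such results. An in-range count probably never reaches the table. Some doubt remains, because Section 9.2.1 and one sentence of Section 9.2.9 omit the out-of-range condition, and the instructions to Appendix B let the table override local normal values where these overlap Grade 1.
- **Screening.** A reader might also infer that the Section 5.3 tolerance would apply to nobody and that eligible people would be turned away. That note covers only minor out-of-range values. The laboratory-based exclusion in the same section requires an abnormality that is clinically significant and that the investigator thinks might interfere with the objectives. Grade alone excludes no one.
- **Use of the faulty line.** The mm³ limits come first in each cell and are usable. If the laboratory reports per mm³, nothing goes wrong.
- **Detection and consequence.** A run of Grade 4 results in healthy adults would be noticed at once, and Section 9.2.9 says that a Grade 4 laboratory value is not in itself an SAE.
- **Timing.** The Phase 3 SAP describes Phase 2 as already conducted, and Phase 3 has no safety laboratory tests, so a correction at that stage protects no further subject. It still matters for how the Phase 2 results were graded.
- **Text extraction.** A fault in reading the PDF cannot be fully ruled out. It is unlikely, because the comma is uniform across the per-litre cells while decimal points survive in the neighbouring rows.

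**Conclusion.** The table is wrong as written, and the matter is minor. In all eight platelet and white-cell cells the per-litre limits are exactly 1,000 times the mm³ limits beside them, and the two lines cannot both hold.

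The practical effect depends on one fact that the documents do not give, the unit in which the Phase 2 laboratory reports. If it is cells/mm³, there is no effect. If it is cells/L and the printed line is followed, every out-of-range low platelet or white-cell count is graded 4, including those that are Grade 1 and not adverse events on the mm³ line. The error is limited to Phase 2 safety laboratory results. It touches no sample size, power or immunogenicity analysis, and no wrongful exclusion has been shown. It needs correcting because the table sets the threshold for laboratory adverse events.

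**What to change.** Reconcile the two lines so that the per-litre figures are the exact equivalents of the mm³ figures already printed:

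- Platelets, x 10⁹/L: Grade 1, 100 to <124.999; Grade 2, 50 to <100; Grade 3, 25 to <50; Grade 4, <25.
- White cells, x 10⁹/L: Grade 1, 2.000 to 2.499; Grade 2, 1.500 to 1.999; Grade 3, 1.000 to 1.499; Grade 4, <1.000.

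These are conversions only. Rounding them, for example to <125 or <2.5, would move a grade boundary and should be avoided. Use one decimal convention throughout the table.

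Then confirm, and record in the study report, which reporting unit and which limits were used to grade the Phase 2 platelet and white-cell results. Regrade any result that was graded on the printed per-litre line.

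The cost is eight table cells and a check of existing Phase 2 grades, with no new procedures for subjects.
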